1.1.3 Afatinib Safety Profile

A **Comprehensive Adverse Events and Potential Risks (CAEPR)** list using NCI Common Terminology Criteria for Adverse Events (CTCAE) terms is included in Section [3.3](#) of the protocol.

Based on phase I studies, the MTD for continuous administration of single agent oral afatinib was 50mg or 40mg daily. The data from the monotherapy trials indicate that the safety profile of afatinib is characterized by significant incidence of dose-dependent gastrointestinal and skin toxicities. The most common toxicities seen are: diarrhea, rash/acne and stomatitis. The majority of these are low grade (grade 1-2).

AEs of special interest

Diarrhea, rash, stomatitis and ILD are considered AEs of special interest because they are either known class effects (*i.e.*, have been observed with other EGFR inhibitors) or are potentially life-threatening (Investigator's Brochure, 2014). The following sections provide integrated summaries for these AEs across different clinical trials, with emphasis on trials using afatinib as monotherapy, especially at the RP2D.

Section [3.4](#) of the protocol has dose modification guidelines for toxicities.

Diarrhea

Diarrhea is the most common AE observed across afatinib monotherapy trials, typically affecting > 80% of patients. Grade 3 diarrhea with the 40mg po qd dose was 15.3% vs 17.2% with the 50mg po qd dose. The majority of patients (> 70%) experienced diarrhea within 14 days of starting afatinib. Grade 3 diarrhea most frequently occurred within the first 6 weeks of treatment. Risk factors for grade 3 diarrhea included: low body weight (< 50kg), females, and low baseline renal function (CrCl < 80mL/min). SAE of diarrhea were reported in 4-7% of patients and grade 5 diarrhea has been reported. Dehydration and renal impairment have both been reported related to diarrhea. Proactive management of diarrhea including adequate hydration and antidiarrheal agents (i.e. loperamide) is important and should be started at first signs of diarrhea.

Rash/Acne

Rash/acne is one of the most common AE reported in patients on afatinib trials with the total incidence reaching 90% in the pivotal NSCLC trial using afatinib monotherapy at 40mg po qd. Grade 3 rash/acne was similar at 40mg and 50mg (14 and 16.2%, respectively). In general, rash manifests as a mild or moderate erythematous and acneiform rash, which may occur or worsen in areas exposed to sun. The majority of patients experienced onset of rash/acne within the first 4 weeks of treatment (79.7% at 40mg and 65.1% at 50mg). Risk factors for grade 3 events included low body weight (< 50kg) and low baseline renal function(<80mL/min). Protective clothing, and/or use of sun screen is advisable. Early intervention (e.g. emollients, antibiotics) of dermatologic reaction is also recommended. Dose reduction allowed successful management of rash in the majority of cases. Rare cases of bullous, blistering and exfoliative skin conditions have been reported including cases suggestive of Stevens-Johnson syndrome. Afatinib should be interrupted or discontinued if these occur.

Palmar-plantar erythrodysesthesia syndrome was also reported as a dermatologic AE with afatinib at rates of 6.6-7.7%. The majority were grade 1-2, but grade 3 events have been reported.

Interstitial Lung disease (ILD)

ILD or ILD-like events are a well-described, infrequent risk of EGFR inhibitors. There have been reports of ILD or ILD-like events in 1.5% of afatinib treated patients. The rate of these events is similar to that observed with other EGFR inhibitors. Careful assessment of all patients with an acute onset and/or unexplained worsening of pulmonary symptoms (dyspnea, cough, fever) should be performed to exclude ILD. Treatment should be interrupted pending investigation of these symptoms. If ILD is diagnosed, afatinib should be permanently discontinued and appropriate treatment instituted as necessary.

Hepatic Adverse Events

Hepatic AEs include elevated hepatic enzymes, which are primarily grade 1-2 and did not lead to treatment discontinuation. In the entire afatinib exposed population, 10.8% (95% CI 10.1-11.7%) were reported with AEs indicative of hepatic impairment with 8 pts with hepatic AEs leading to death. These were considered not related to afatinib in 5 patients (related to progressive disease or sepsis). Drug-related fatal case of acute hepatic failure has been reported. Periodic liver function testing is recommended in patients treated with afatinib.

Keratitis

Keratitis and ulcerative keratitis have been reported with the EGFR inhibitors. In 6,002 afatinib treated patients, 39 (0.6%) cases were identified.

Effect on QTc

A phase II study in patients with advanced solid tumors investigated the effect of afatinib on the QTc interval. Afatinib at doses of 50mg daily did not prolong the QT interval or the heart rate corrected QT interval (QTcF). It did not affect heart rate. No other clinically meaningful changes in QTcF or ECG endpoints were observed.

Events of cardiac dysfunction/LVEF decrease

Left ventricular ejection fraction (LVEF) decrease has been reported with agents targeting HER2, in particular with the monoclonal antibody, trastuzumab. In the phase IIb/III trial in advanced NSCLC using afatinib 50mg, 4 (1.0%) afatinib treated patients vs 1 (0.5%) placebo patients experienced an AE of cardiac failure, cardiopulmonary failure, hepatic congestion or left heart failure. This was a non-significant difference (HR 1.32, 0.14-12.50).³⁷ In study 1200.32, with 40mg of afatinib, the frequency of these AEs was 2.6% in the afatinib arm vs 0.9% in the chemotherapy arm. This was not significantly increased when corrected for time at risk (HR 1.18, 0.12-11.39). Furthermore, the heart failure or LVEF decrease events were all grade 2 or lower.³⁵

2. Selection of Patients

Each of the criteria in the checklist that follows must be met, along with the eligibility in the MATCH Master Protocol, in order for a patient to be considered eligible for this study. Use the checklist to confirm a patient's eligibility. For each patient, this checklist must be photocopied, completed and maintained in the patient's chart.

In calculating days of tests and measurements, the day a test or measurement is done is considered Day 0. Therefore, if a test is done on a Monday, the Monday four weeks later would be considered Day 28.

ECOG-ACRIN Patient No. _____

Patient's Initials (L, F, M) _____

Physician Signature and Date _____

NOTE: Policy does not allow for the issuance of waivers to any protocol specified criteria (http://ctep.cancer.gov/protocolDevelopment/policies_deviations.htm). Therefore, all eligibility criteria listed in Section 2 must be met, without exception. The registration of individuals who do not meet all criteria listed in Section 2 can result in the participant being censored from the analysis of the study, and the citation of a major protocol violation during an audit. All questions regarding clarification of eligibility criteria must be directed to the Group's Executive Officer ([contact]) or the Group's Regulatory Officer ([contact]).

NOTE: Institutions may use the eligibility checklist as source documentation if it has been reviewed, signed, and dated prior to registration/randomization by the treating physician.

NOTE: All patients must have signed the relevant treatment consent form

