3.4 Dose Modifications

All toxicity grades below are described using the NCI Common Terminology Criteria for Adverse Events (CTCAE) version 4.0.

All appropriate treatment areas should have access to a copy of the CTCAE version 4.0. A copy of the CTCAE version 4.0 can be downloaded from the CTEP website (<http://ctep.cancer.gov>).

Afatinib will be administered at the recommended dose of 40 mg orally once daily starting on the first day of administration and continue until disease progression or unacceptable toxicity. We chose the 40 mg daily dose since the Css still remains adequate at this dose. With the 50 mg dose used in previous trials of afatinib in HER2+, patients showed poor tolerability data. High Rates of dose modification were seen in previous studies with 50 mg daily dosing.

Afatinib will not be held for hematologic toxicity, unless it is determined to be a drug-related grade 3 or 4 hematologic event.

Treatment may be delayed by 2 weeks due to toxicity. If treatment is delayed beyond 2 weeks the subject will come off study for unacceptable toxicity.

Discontinuation of afatinib for any reason for longer than 2 weeks will result in removal of the patient from this subprotocol.

The afatinib dose may be adjusted according to individual patient tolerance as outlined below.

Table 1. Dose Levels for Afatinib

Dose Level	Daily Dose/ Route	Dispensed As	Schedule
Starting dose level: 0	40 mg, PO	1 × 40-mg tablet	Daily during 4-week cycle
-1	30 mg, PO	1 × 30 mg tablet	Daily during 4-week cycle
-2	20 mg, PO	1 × 20-mg tablet	Daily during 4-week cycle

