3.4.3 Dose reduction for afatinib

Intra-patient dose reduction by 1, and if needed 2, dose-levels will be allowed depending on the type and severity of toxicity encountered provided that criteria for patient withdrawal from study treatment have not been met. Intrapatient dose re-escalation is not allowed.

All intra-patient dose reductions are relative to the lowest dose level of the current cycle.

Recovery to acceptable levels of toxicity must occur within 2 weeks to allow continuation in the study.

No more than 2 dose reductions are permitted for any patient. If further dose reduction is required, the patient must be removed from the study.

The following table describes the recommended dose modifications for study treatment associated toxicity:

Table 2. Dose Modification for Afatinib

Toxicity	Grade 1	Grade 2	Grade 3	Grade 4
Non-hematologic Toxicity (except specific toxicities mentioned below) ^{a,b,c}	Continue at the same dose level.	Continue at the same dose level.	Withhold dose until toxicity is grade ≤ 1 or has returned to baseline. Then reduce the dose by 1 level and resume treatment.	Withhold dose until toxicity is grade ≤ 1 or has returned to baseline. Then reduce the dose by 1 level or discontinue treatment (discretion of the investigator).
Cardiac Toxicity	Continue at the same dose level.	Continue at the same dose level except for asymptomatic decrease of LVEF by an absolute value of 20% (or more) and to $<$ institutional LLN. Withhold dose until toxicity is grade ≤ 1 . Then reduce dose by 1 level and resume treatment.	Discontinue study treatment.	Discontinue study treatment.
Renal Toxicity	Continue at the same dose level.	Withhold dose until toxicity is grade ≤ 1 . Then reduce dose by 1 level and resume treatment.	Withhold dose until toxicity is grade ≤ 1 . Then reduce dose by 1 level and resume treatment.	Withhold dose until toxicity is grade ≤ 1 . Then reduce dose by 1 level and resume treatment or discontinue treatment (discretion of the investigator).
Diarrhea	Continue at the same dose level. ^b	Continue at the same dose level unless diarrhea persists for 2 or more days despite adequate anti-diarrheal medication or hydration. Withhold dose until toxicity is grade ≤ 1 . Then reduce dose by 1 level and resume treatment.	Withhold dose until toxicity is grade ≤ 1 . Then reduce dose by 1 level and resume treatment.	Withhold dose until toxicity is grade ≤ 1 . Then reduce dose by 1 level and resume treatment.

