Rash (Papulopustular, pustular, acneiform, maculo-papular) ^d	Continue at the same dose level.	Continue at the same dose level unless rash persists and is intolerable or worsens over > 7 days. If this occurs: Withhold dose until toxicity is grade ≤ 1 . Then reduce dose by 1 level and resume treatment.	Withhold dose until toxicity is grade ≤ 1 . Then reduce dose by 1 level and resume treatment.	Discontinue study treatment
Drug-induced hepatic impairment	Continue at the same dose level.	Continue at the same dose level.	Withhold dose until toxicity is grade ≤ 1 or has returned to baseline. Then reduce the dose by 1 level and resume treatment.	Discontinue study treatment

Ulcerative keratitis	Continue at the same dose level.	Continue at the same dose level.	Withhold dose until toxicity is grade ≤ 1 or has returned to baseline. Then reduce the dose by 1 level and resume treatment.	Discontinue study treatment
Interstitial Lung Disease	If a patient develops respiratory problems consistent with possible interstitial lung disease (ILD), afatinib is to be withheld pending a diagnostic evaluation. Afatinib will be discontinued if a diagnosis of ILD is confirmed.			

- a. *No dose modifications will be needed for low electrolytes (Na, K, Phos, Mg) unless the grade 3 or 4 adverse event were to last >48 hours despite optimal electrolyte repletion*
- b. *See supportive care for diarrhea in Section [3.5.1](#)*
- c. *Nausea and vomiting should be graded after maximal medical management*
- d. *See supportive care for rash in Section [3.5.1](#)*

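### The instruction in Section 1.1.3 to interrupt or stop afatinib for bullous, blistering or exfoliative skin conditions is not carried into the dosing rules, which would generally continue the dose if such an event were graded 1 or 2

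*Protocol*

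**What the plan says.** The Rash/Acne part of Section 1.1.3 reports rare bullous, blistering and exfoliative skin conditions, some suggestive of Stevens-Johnson syndrome. It then instructs: "Afatinib should be interrupted or discontinued if these occur". No grade is attached. The same section states that Section 3.4 "of the protocol has dose modification guidelines for toxicities", so a site looking for the dosing rule is sent there.

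In Section 3.4, grading follows an external standard: "All toxicity grades below are described using the NCI Common Terminology Criteria for Adverse Events (CTCAE) version 4.0". Section 3.4.2 orders a hold for drug-related non-hematologic events of grade 3 or 4. Section 3.4.3 introduces Table 2 as follows: "The following table describes the recommended dose modifications for study treatment associated toxicity".

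Table 2 has no row for bullous, blistering or exfoliative conditions. Two rows are candidates:

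- The general row, "Non-hematologic Toxicity (except specific toxicities mentioned below", continues the same dose at grades 1 and 2.
- The row labelled "Rash (Papulopustular, pustular, acneiform, maculo-papular" continues at grade 1. Its grade 2 cell reads: "Continue at the same dose level unless rash persists and is intolerable or worsens over > 7 days".

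The rash guidance in Section 3.5.1 does not mention these conditions either.

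**The concern.** The safety text tells the site to act as soon as such a condition appears. The dosing table, read by grade, tells the site to carry on at the lower grades. Nothing in this document says which of the two prevails.

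What is at stake is patient safety. A site dosing from Table 2 alone could keep giving afatinib during an early blistering or exfoliative reaction. Another site, following Section 1.1.3, would hold the drug for the same event.

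The treatment of interstitial lung disease (ILD) suggests an oversight and not a deliberate choice. Section 1.1.3 gives an interrupt-or-discontinue instruction for ILD too. That instruction was carried into Table 2 as a row without grades: "afatinib is to be withheld pending a diagnostic evaluation".

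**Working it through.** No arithmetic applies. The check sets the texts side by side by grade, for an event that is bullous, blistering or exfoliative.

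| Grade | Section 1.1.3 | Table 2, general row | Table 2, Rash row | Result |
|---|---|---|---|---|
| 1 | Interrupt or discontinue | Same dose | Same dose | Conflict under either row |
| 2 | Interrupt or discontinue | Same dose | Same dose, unless the rash persists and is intolerable or worsens over more than 7 days; then withhold and reduce | Conflict under the general row, and under the Rash row outside its exception |
| 3 | Interrupt or discontinue | Withhold, then resume one level lower | Withhold, then resume one level lower | Consistent |
| 4 | Interrupt or discontinue | Withhold, then reduce or discontinue | Discontinue | Consistent |

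**Which row applies?** The Rash row's label names four types of rash and none of these conditions. Footnote 8 of the adverse event list in Section 3.3 counts skin exfoliation as rash, which might lead a site to that row. The footnote is a reporting grouping, however, and not a dosing rule. On the labels alone the general row is the better fit. The conflict at grade 1 does not depend on the choice.

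**Can such events be graded 1 or 2?** The document does not establish this, because the CTCAE 4.0 definitions are not reproduced. The only internal evidence is indirect. The rash category that includes skin exfoliation has a grade 2 threshold for the exception from expedited reporting, so the protocol expects some events in that category at grade 2 or below. The threshold belongs to the whole category and proves nothing about any one condition. That list also uses CTCAE 5.0 terms, while the dosing grades use version 4.0.

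**Does any other text close the gap?** Section 3.4.2 repeats the restriction of the general hold to grades 3 and 4. Section 3.5.1 says that grade 1 rash may not need treatment, and leaves a pause for persistent, poorly tolerated grade 2 rash to the investigator's choice. Section 3.6 allows stopping for unacceptable toxicity, or where the protocol's constraints harm the patient, but names no skin condition.

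**How often?** No rate is given for these conditions as a group, and none by grade. The share graded 1 or 2 could lie anywhere from 0% to 100%. At 0% there is no conflict in practice.

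**The case against.** The strongest reply is that the two texts can be read together. Section 1.1.3 gives a specific instruction for named conditions, whereas the general row is a catch-all in a table of recommended modifications. A specific rule normally governs over a catch-all. Section 3.4.3 also ties dose reduction to the type of toxicity as well as its severity. A site that holds the drug therefore breaks no rule, and Section 3.6 gives it further room. This stands, and it limits the weight of the point. It does not remove the conflict, because Section 1.1.3 itself names Section 3.4 as the place for dose modification, and the instruction is absent there.

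A second reply is that these events are likely to be severe. Section 1.1.3 sets them apart from ordinary mild or moderate rash, and Section 3.3 lists Stevens-Johnson syndrome and toxic epidermal necrolysis as rare but serious. If none were graded below 3, the table would already match the safety text. This also stands as a limit, which is why the point is conditional.

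A third reply is that the MATCH Master Protocol, which is used together with this subprotocol, may contain a rule of precedence. It is not at hand, so the statement that no text settles the matter covers this document only.

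A reader might go further and infer that the protocol obliges sites to keep dosing patients who have Stevens-Johnson syndrome or toxic epidermal necrolysis. The document does not support that. It does not show that either would be graded 1 or 2, and continuation is not forced at any grade.

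**Conclusion.** The point holds as a low-frequency safety inconsistency. Section 1.1.3 gives an instruction without a grade limit, and the operative dosing section omits it. The two texts diverge at grade 1 under either candidate row, and at grade 2 under the general row or under the Rash row outside its exception. They agree at grades 3 and 4.

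The conclusion rests on one assumption that the document supports only indirectly: that some of these events are graded 1 or 2. No count of affected patients can be given. A reader might apply the less-than-3% column of the adverse event list to the accrual goal of 70. That column covers the two named severe forms, which are not shown to fall in the conflicting grades, so the product would not measure this problem.

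The matter does not touch the accrual goal or any efficacy calculation. It is still worth correcting, because the consequence for a single patient could be serious and the correction is small.

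**What to change.** Add to Table 2, by addendum, a row or footnote that applies at any grade and expressly overrides the general and Rash rows for bullous, blistering or exfoliative skin conditions:

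- **Suspected:** withhold afatinib pending evaluation.
- **Stevens-Johnson syndrome or toxic epidermal necrolysis suspected or confirmed:** discontinue permanently.
- **Another such condition confirmed:** interrupt until grade 1 or lower and resume one dose level lower, or discontinue, within the 2-week limit of Section 3.4. An event that is grade 1 at onset meets this threshold at once, so the clinical leads should decide whether to require full resolution in that case.
- **Ruled out:** resume at the same dose unless another row applies. State this as an express exception to the sentence in Section 3.5.1 that reduces the dose after a treatment pause. Without the exception, a purely diagnostic hold would become a permanent reduction, because Section 3.4.3 bars re-escalation.

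The ILD row is a useful model for the layout only. Section 3.5.1 calls for discontinuation when ILD is merely suspected, whereas the row withholds first, so the new text should spell out suspected and confirmed cases separately, as above.

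The cost is one row or footnote and one stated exception, with no added scheduled visits or patients. The downside is a few short dose holds for skin events later found benign. The evaluation must also finish within 2 weeks, because Section 3.4 removes patients whose interruption lasts longer.

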2.1 Eligibility Criteria

Rev.2/16
Rev.2/16
Rev.2/16
Rev.Add13

- _____ 2.1.1 Patients must fulfill all eligibility criteria outlined in Section 3.1 of MATCH Master protocol (excluding Section 3.1.6) at the time of registration to treatment step (Step 1, 3, 5, 7).
- _____ 2.1.2 Patient's tumor must have activating HER2 mutation, as determined via the MATCH Master Protocol and according to Appendix III. Additionally, any in-frame insertions in exon 20 will be considered an activating mutation. See [Appendix III](#) for information on the targeted mutations and the corresponding Levels of Evidence (LOE).
- _____ 2.1.3 Patients must have an electrocardiogram (ECG) within 8 weeks prior to treatment assignment and must have no clinically important abnormalities in rhythm, conduction or morphology of resting ECG (e.g. complete left bundle branch block, third degree heart block). Date of ECG: _____
- _____ 2.1.4 Patients with known left ventricular dysfunction must have ECHO or a nuclear study (MUGA or First Pass) within 4 weeks prior to registration to treatment and must not have left ventricular ejection fraction (LVEF) < institutional lower limit of normal (LLN). If the LLN is

not defined at a site, the LVEF must be > 50% for the patient to be eligible.

Date of ECHO/nuclear study: _____

NOTE: Pre-treatment LVEF determination in patients without known left ventricular dysfunction is NOT otherwise required.

- _____ 2.1.5 Patients must not have known hypersensitivity to afatinib or compounds of similar chemical or biologic composition.
- _____ 2.1.6 Patients must have \leq Grade 1 diarrhea at baseline.
- _____ 2.1.7 Patients with a history of interstitial lung disease will be excluded.
- _____ 2.1.8 Patients must not have had prior treatment with any of the following TKIs, which have known activity against HER2 kinase:
 - Neratinib
 - AC-480 (BMS-599626)
 - AST 1306
 - Canertinib (CI 1033)
 - CUDC-101
 - Lapatinib
 - TAK285
 - Afatinib
 - AEE 788
 - AZD8931
 - CP-724714
 - Dacomitinib
 - Perlitinib
- _____ 2.1.9 Patients must have \leq Grade 1 renal function as defined below:
Creatinine \leq 1.5 x normal institutional limits
OR
Measured Creatinine clearance \geq 60 mL/min/1.73 m² for patients with creatinine levels above institutional normal or as calculated by the Cockcroft-Gault Equation.
Creatinine clearance: _____
The above renal eligibility criteria should be strictly followed and will override the MATCH Master Protocol requirements.
- _____ 2.1.10 Patients with non-small cell lung cancer will be excluded.

Physician Signature

Date

OPTIONAL: This signature line is provided for use by institutions wishing to use the eligibility checklist as source documentation.

3. Afatinib Treatment Plan

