Less than 5% of a single dose afatinib is excreted via the kidneys. The safety, pharmacokinetics and efficacy of afatinib have not been studied in patients with renal impairment. In the PopPK analysis, exposure to afatinib slightly increased with lowering the creatinine clearance (CrCL), *i.e.* for a patient with a CrCL of 60 or 30 mL/min exposure (AUC_{T,ss}) to afatinib increased by 13% and 42%, respectively, and decreased by 6% and 20% in patients with a CrCL of 90 or 120 mL/min, respectively, compared to a patient with the CrCL of 79 mL/min (median within analyzed population). As the effect sizes were within the observed inter-patient variability of exposure, no dose adjustment is considered necessary in patients with mild or moderate renal impairment.

Population PK: No statistically significant effect was seen based on smoking status, ethnic origin, age, liver metastases or liver function parameters. Predicted individual effects are considered to be mild to moderate for creatinine clearance, gender, body weight, ECOG performance status, alkaline phosphatase, lactate dehydrogenase and total plasma protein levels.

Although several phase II studies used 50 mg daily, the phase I data confirms that Css at 40 mg exceeds IC₅₀ for HER2, thus this will be the starting dose for this subprotocol.⁴⁴

Table 1: Comparison of gMean pharmacokinetic parameters of afatinib in cancer patients for the 20mg, 30mg, 40 mg and 50mg dose group and for the whole dose range (10-100mg) from 5 monotherapy trials²³.

Afatinib BS	20mg		30mg		40mg		50mg		Overall (10 – 100mg)	
	N	gMean (gCV%)	N	gMean (gCV%)	N	gMean (gCV%)	N	gMean (gCV%)	N	gMean
AUC ₀₋₂₄ [ng·h/mL]	12	119 (56.6)	10	189 (95.9)	30	324 (68.9)	69	459 (68.0)		
AUC _{t,ss} [ng·h/mL]	15	380 (77.2)	8	660 (92.4)	26	631 (85.9)	51	1130 (59.6)		
C _{max} [ng/mL]	13	11.6 (85.1)	10	16.3 (139)	30	25.2 (73.3)	73	40.8 (76.6)		
C _{max,ss} [ng/mL]	15	24.5 (88.5)	8	46.5 (120)	27	38.0 (105)	51	77.0 (63.6)		
t _{max} [h] a	13	3.00 (0.500 - 24.0)	10	2.00 (0.567 - 692)	30	3.98 (0.583 - 9.10)	73	3.13 (0900 - 9.05)	189	3.02 (0.467 - 24.0)
t _{max,ss} [h] a	15	4.98 (0.500 - 9.08)	8	2.01 (0.517 - 4.00)	27	2.98 (0.467 - 23.8)	51	3.82 (1.00 - 7.05)	149	3.00 (0.467 - 23.8)
t _{1/2} [h]	11	22.3 (80.3)	10	21.3 (82.1)	30	26.9 (61.1)	13	21.9 (54.8)	127	21.4 (56.5)
t _{1/2,ss} [h]	15	47.1 (51.6)	7	33.4 (56.8)	23	36.3 (57.1)	7	22.3 (25.4)	100	37.2 (45.5)
CL/F [mL/min]	11	1430 (64.7)	10	1370 (72.9)	30	952 (86.2)	13	1090 (94.0)	127	1050 (76.3)

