4.1 Therapeutic Parameters for Afatinib Treatment

NOTE: In addition to the study parameters listed in the MATCH Master Protocol, the below parameters must also be performed for patients receiving afatinib treatment.

NOTE: All assessments required prior to registration to treatment should be done \leq 4 weeks prior to registration to Steps 1, 3, 5, 7, excluding the radiologic evaluation and electrocardiogram (ECG).

Test/Assessment	Prior to Registration to Treatment	Treatment			End of Treatment	Follow Up ^F
		Cycle 1, day 8 and day 15 ^G	Every Cycle, prior to treatment	Every 2 Cycles		
H&P, Weight, Vital signs ^A	X		X ^J			X
Performance status	X	X	X ^J			X
CBC w/diff, plt ^B	X		X ^J			X
Serum chemistry ^B	X		X ^J			X
Radiologic evaluation ^D	X			X ^D		X ^F
β -HCG ^C	X					
Toxicity Assessment ^G		X	X		X	X ^F
Pill Count/Diary ^H			X		X	
ECG ^K	X		X ^I			
Echocardiogram or Nuclear Study ^K	X ^I		X ^I			X ^I
Tumor biopsy and blood sample for MATCH Master Protocol ^E				X	X	

^A. History and physical, including vital signs and weight at the start of each cycle (up to 3 days before start of new cycle).

^B. Albumin, alkaline phosphatase, total bilirubin, bicarbonate, BUN, calcium, creatinine, glucose, phosphorus, potassium, SGOT[AST], SGPT[ALT], sodium, magnesium and serum tumor markers (including LDH, PSA if appropriate). For eligibility purposes, participants with creatinine levels above institutional normal, Cockcroft-Gault will be used to calculate creatinine clearance. CBC w/diff, platelets and serum chemistries should be performed on cycle 1, day 1 (or up to 7 days prior), and at the start of each subsequent cycle (up to 3 days before start of new cycle). CBC with differential will be performed more frequently in patients with grade 4 neutropenia or thrombocytopenia until resolution to \leq grade 3. CBC and serum chemistries are only required in follow-up until values return to pre-treatment levels or until progressive disease.

^C. Blood pregnancy test (women of childbearing potential) required prior to beginning treatment.

^D. Disease measurements are repeated every 2 cycles for the first 26 cycles, and every 3 cycles thereafter until PD or start of another MATCH treatment step. The baseline evaluation should be performed as closely as possible to the beginning of treatment and never more than 6 weeks

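### Does criterion 2.1.9 leave renal eligibility undecided, through its OR, its clearance method and its unit?

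*Protocol*

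**What the plan says.** Section 2.1.9 has two limbs, with OR printed on a line of its own between them. The first is creatinine no higher than "1.5 x normal institutional limits". The second is a measured clearance of at least 60 mL/min/1.73 m² "for patients with creatinine levels above institutional normal or as calculated by the Cockcroft-Gault Equation". The criterion closes with "The above renal eligibility criteria should be strictly followed and will override the MATCH Master Protocol requirements".

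Footnote B to the assessment table in section 4.1 adds: "For eligibility purposes, participants with creatinine levels above institutional normal, Cockcroft-Gault will be used to calculate creatinine clearance". It states no cut-off and does not mention measured clearance.

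The note on waivers in section 2 allows no exceptions. It warns that registering a patient who does not meet the criteria "can result in the participant being censored from the analysis of the study", and it sends questions about criteria to the group's executive or regulatory officer.

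The pharmacokinetic background in section 1.1.2.1 gives clearance in mL/min, without indexing ("for a patient with a CrCL of 60 or 30 mL/min exposure").

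**The concern.** Three features look unreconciled.

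- **Logic.** The clearance limb and footnote B both address patients from 1.0 x normal upward, but the creatinine limb has already admitted everyone up to 1.5 x. In that band a clearance is requested that decides nothing. A reader could suspect that clearance was meant to decide for everyone above normal and that the OR is a mistake.
- **Method.** Section 2.1.9 accepts a measured or a calculated clearance. Footnote B names only Cockcroft-Gault.
- **Unit.** The cut-off is per 1.73 m², the named equation conventionally gives mL/min, and no indexing to body surface area is stated.

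The criterion is to be applied strictly, overrides the master protocol and cannot be waived. If two sites judged the same patient differently, one might register a patient whom an auditor later calls ineligible, and that patient could be dropped from the analysis. With an accrual goal of 70, a few such patients would be noticed.

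**Working it through.** The protocol gives no figure to reproduce. The check is a truth table, followed by worked patients. Patient profiles and upper limits of normal (ULN) are assumed: 0.9-1.1 mg/dL for women and 1.1-1.3 for men.

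**Logic.** Let r = creatinine / institutional normal and c = clearance. As printed, a patient is eligible if r ≤ 1.5, or if r > 1 and c ≥ 60. The rival reading lets clearance decide for everyone above normal: eligible if r ≤ 1, or if c ≥ 60.

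| r | c | As printed | Rival reading |
|---|---|---|---|
| 1.2 | 40 | eligible | not eligible |
| 1.2 | 60 or 80 | eligible | eligible |
| 1.5 | 40 | eligible | not eligible |
| 1.6 | 40 | not eligible | not eligible |
| 1.6 | 60 or 80 | eligible | eligible |

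The readings part only in the 1.0-1.5 band with low clearance. The rival reading requires striking out the printed OR, and no passage states it. Footnote B has no threshold, so it cannot supply one. As printed, every combination has an answer.

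**Method.** Section 2.1.9 allows a measured value or Cockcroft-Gault. Footnote B says which equation to use when clearance is calculated. Read together: measured or, if calculated, Cockcroft-Gault.

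**Unit.** Formulas (standard, not printed in the protocol):

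- CG = (140 − age) × kg × (0.85 if female) / (72 × creatinine)
- BSA = √(cm × kg / 3600)
- indexed value = CG × 1.73 / BSA

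The two units disagree only when the unindexed value lies between 60 and 60 × BSA/1.73. That interval is 52.0-60 at BSA 1.5, empty at 1.73, 60-69.4 at 2.0 and 60-76.3 at 2.2 m².

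Two assumed patients above 1.5 x normal, where clearance decides:

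- Man, 45 y, 110 kg, 183 cm, 1.7 x ULN (creatinine 1.87-2.21): 95 × 110 / (72 × 1.87) = 77.6 and 95 × 110 / (72 × 2.21) = 65.7 mL/min. BSA = √(183 × 110/3600) = 2.365. Indexed: 56.8 and 48.0. The unit decides.
- Man, 55 y, 95 kg, 180 cm, creatinine 1.75 with ULN 1.15 (1.52 x): 85 × 95 / (72 × 1.75) = 64.1 mL/min. BSA = 2.18. Indexed: 50.9. The unit decides.

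Four assumed patients at 1.2 x ULN:

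- Woman, 75 y, 55 kg: 32.0-39.1 mL/min
- Woman, 70 y, 60 kg: 37.6-45.9 mL/min
- Man, 70 y, 75 kg: 46.7-55.2 mL/min
- Man, 25 y, 52 kg, 165 cm, creatinine 1.44: 57.7 mL/min (64.6 indexed)

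All four are eligible on creatinine alone. Neither clearance nor its unit affects them under the printed rule.

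**How far the unit effect reaches.** Take creatinine just above 1.5 x a ULN of 1.1, that is 1.65 mg/dL.

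- Man of 75 kg, 175 cm (BSA 1.909): unindexed 60 needs 140 − age ≥ 60 × 72 × 1.65/75 = 95.0, so age up to about 45. Indexed 60 means 66.2 mL/min, so 140 − age ≥ 66.2 × 72 × 1.65/75 = 104.9, age up to about 35. The units disagree between about 35 and 45 years.
- Man of 110 kg, 183 cm: unindexed needs 140 − age ≥ 60 × 72 × 1.65/110 = 64.8, age up to about 75. Indexed 60 means 82.0 mL/min, so 140 − age ≥ 82.0 × 72 × 1.65/110 = 88.6, age up to about 51. The units disagree between about 51 and 75 years.

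Among men, therefore, the effect needs clearly raised creatinine together with either large body size or fairly young age.

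**The case for a change.** The strongest case for a change is that a criterion described as strict, with no waivers and with priority over the master protocol, ought to give one answer per patient on its face. The master protocol's renal rule cannot settle the matter. The unit point does not depend on how the OR is read: above 1.5 x normal, clearance is the only way in, and the two worked men pass or fail on the unit alone. The officers can help only if a site notices the ambiguity, and the correction would cost one criterion and one footnote.

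The unit observation stands. The pairing of an indexed cut-off with Cockcroft-Gault is loose, and the protocol does not say how to bridge it. The rest is weaker. In the 1.0-1.5 band, an auditor would have no text on which to fault a patient who meets the printed creatinine limb. Footnote B does not forbid measured clearance, and no example shows method alone altering eligibility. The cut-off itself carries a single unit, and no other eligibility text contradicts it. The mL/min figures elsewhere are pharmacokinetic and safety background. There is no evidence that sites have in fact diverged.

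**Conclusion.** The wording is redundant in one place, incomplete in another and loose about a unit, but it contains no contrary rule. Followed as printed, it gives a usable decision: creatinine up to 1.5 x normal suffices, and above that a clearance of 60 per 1.73 m² is required. A site that calculates clearance can index it to match the stated unit or ask the group's officers. This is a drafting slip that careful users can resolve.

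The possible effect is confined to patients above 1.5 x normal whose clearance lies between 60 and 60 × BSA/1.73 mL/min, for example 60-76.3 at a BSA of 2.2 m². The protocol gives no distribution of creatinine or body size, so the number among 70 cannot be computed. No endpoint, estimate or conclusion is shown to change.

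Nor is a material safety gain shown. Section 1.1.2.1 puts exposure 13% higher at a clearance of 60 and 42% higher at 30 mL/min than at the median of 79, within inter-patient variability, and states that "no dose adjustment is considered necessary in patients with mild or moderate renal impairment".

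This conclusion assumes the standard Cockcroft-Gault formula and the profiles and ULNs listed above. It takes no view on where the renal limit should lie.
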